12.1.3. Record keeping / archiving	35
12.2 Data management	36
12.2.1 Data Management System	36
12.2.2 Data security, access and back-up	36
12.2.3 Analysis and archiving	36
12.2.4 Electronic and central data validation	36
12.3 Monitoring	36
12.4 Audits and Inspections	36
12.5 Confidentiality, Data Protection	36
12.6 Storage of biological material and related health data	37
13. PUBLICATION AND DISSEMINATION POLICY	37
14. FUNDING AND SUPPORT	37
14.1 Funding	37
14.2 Other Support	37
15. INSURANCE	37
16. REFERENCES	37
17. APPENDIX	39

STUDY SYNOPSIS

Sponsor-Investigator	[name]. med. [name]
	Leitender Arzt, Zentrum für Integrative Gastroenterologie
	Leiter, Magen Darm Funktion: Basel, Labor und Klinik für funktionelle Magendarm Erkrankungen und Motilitätsstörungen
Study Title:	Perceived Changes in Symptom Burden and physiological effects of a proprietary phyto-therapeutic preparation (Amara) in patients with functional dyspepsia: Prospective study as Investigator Initiated Trial (IIT)
Short Title / Study ID:	Amara bei Dyspepsie, Amara-KLA-01-22
Protocol Version and Date:	Version 1.4, 10.11.2023
Trial registration:	Clinicaltrials.gov ID: NCT05553587
Study category and	Risk category A acc. to ordinance HRO Art.7
Rationale	The investigational drug is approved with a reduced dossier without indication according to Art. 25 para. 1 KPAV (SR 812.212.24). This study follows the indication text licensed by Swissmedic: " Weleda Amara-Drops can be used for digestive complaints such as heartburn, flatulence and bloating after meals, to stimulate the bile flow and for loss of appetite and nausea. The effect of Weleda Amara drops is based on a balanced mixture of medicinal plants with tonic (invigorating) and aromatic bitter substances, which are suitable for stimulating digestion." Further, no side effects have been reported in past studies so far. All these reasons lead us to the conclusion that this study is only associated with minimal risks and should be classified in risk category A.
Clinical Phase:	Confirmatory Trial (Phase IV)

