Study Product / Intervention:	In this study the test medication (Amara drops) will be taken by the participants before meals. The herbal preparation is manufactured by Weleda AG, Arlesheim. Besides the bitter substances Artemisia absinthium, Cichorium intybus, Juniperus and Gentiana lutea, Amara Drops contain also Centaurium, Peucedanum, Achillea millefolia, Salvia officinalis and Taraxacum, all suspended in an alcohol-based tincture. The full indication text licensed by Swissmedic is: "According to the anthroposophical knowledge of man and nature, Weleda Amara-Drops can be used for digestive complaints such as heartburn, flatulence and bloating after meals, to stimulate the bile flow and for loss of appetite and nausea. The effect of Weleda Amara drops is based on a balanced mixture of medicinal plants with tonic (invigorating) and aromatic bitter substances, which are suitable for stimulating digestion. Weleda Amara drops mildly stimulate the secretion of saliva and gastric juices, promote the formation and secretion of bile and thus facilitate the digestion of fats. In addition, they are effective against flatulence and cramps."
Control Intervention:	No control group
Number of Participants with	Participants: 60 patients with functional dyspepsia with postprandial distress (Rome IV criteria).
Rationale:	There are no previous studies that have assessed the effect of Amara Drops in functional dyspepsia. Before randomized double blind controlled studies can be considered it is appropriate to assess perceived changes in symptom burden and physiological effects of Amara in clinical practice. At the same time the feasibility of recruiting this patient group and performing gastric emptying and other studies will be assessed. In this prospective open label study, placebo effects are likely to be present. Previous randomized controlled trials indicate that this can be up to 40%. To demonstrate convincing evidence of clinical efficacy a minimum 60% response rate above no treatment (run-in phase) must be demonstrated. Based on these considerations, for the primary outcome, power calculation suggests that at least 58 patients are required to detect moderate effects on perceived symptom burden at a convincing level of statistical significance (beta 0.9, alpha <0.01).
Study Duration:	2 years

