5. STUDY OUTCOMES

5.1 **Primary Outcome**

The primary outcome will be the perceived change of dyspeptic symptoms assessed by the Leuven Dyspepsia Questionnaire (LDQ) between visit 1 (off treatment) and 3 (after treatment). The questionnaire contains 3 domains/questions which related to: a) The inability to finish a meal due to early satiety b) The feeling of food lying heavily in the stomach c) Feeling bloated in the stomach. The questionnaire is presented to the patients in the form of three questions which define five grades of severity (0-4), and which are supported by pictograms expressing the associated severity. Higher total scores indicate more severe dyspeptic symptoms. For each subscale 0 normal, 1 mild dyspepsia; 2, moderate dyspepsia; 3, severe dyspepsia; 4, very severe dyspepsia. The questionnaire is to be evaluated on a daily basis and the mean of the values of the three symptoms is proposed to represent the severity of that day. A weekly score can be calculated from the daily scores and is currently proposed for the primary use of the scale.(21)

The LDQ has been developed using standard methods, including focus group interviews and cognitive debriefing interviews.(21) The further validation of the score was undertaken with the means of interventional studies, evaluating the response of this questionnaire to prokinetic and neuromodulatory medications. The LDQ has shown to be a good rating scale to be used as a severity indicator of dyspepsia and can be given to the same patient in subsequent sessions to track the change in symptoms. A minimally clinically important difference has also been determined. The results of this validation work have been published in peer reviewed journals.(22, 23)

The Leuven Postprandial Distress Scale, which is supported by the European Medicines Agency, is a sensitive and reliable patient-reported outcome instrument to assess symptoms in the functional dyspepsia/postprandial distress syndrome. Based on this information, the LDQ variable will be the main result to verify whether the test medication in this trial is efficacious. In this open-label study in which placebo and treatment effects are summed we expect a moderate to large >60% reduction in mean symptom burden as measured by the LDQ (results will be shown as mean \pm SD).

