- In addition to subjective patient related outcome measures, repeat ¹³C breath testing with the Nottingham Test Meal on and off treatment will provide physiological assessment of effects of Amara on gastric motor and sensory function. Continuous assessment of patient sensations during Drink tests (i.e., gastric filling) may be less impacted by patient recall than questionnaires. ¹³C breath testing provides an indirect assessment gastric emptying based on the excretion of ¹³CO₂ in the expired air. Although well validated against scintigraphy, it remains uncertain to what extent these results can be affected by individual patient factors other than gastric emptying (e.g. metabolism). Note that this limitation will not affect the results of this study because we will compare gastric emptying in patients on and off Amara treatment (i.e., patients act as their own control).
- Amara drops will be distributed for self-administration at home, thus, we rely on participants to report their intake accurately. Compliance will be checked as described above.
- The four-week duration of drug intake is relatively brief and may underestimate the treatment effect.
- This study may suffer from the limitation that participants will take other over the counter medications or engage in other treatments at home.
- This study design does not allow evaluating the efficacy of Amara medication. However, the aim of this prospective study is to acquire results on overall effectiveness that will inform the design of a randomized controlled study with this aim.

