11. STATISTICAL METHODS

11.1 Hypothesis

Null hypothesis: There will be no difference in the primary outcome (LDQ score) between baseline and after four weeks of Amara treatment.

Alternative hypothesis: The LDQ score after four weeks treatment is different from the LDQ-score before the treatment.

In the case of statistical significance, the null hypothesis is rejected and the described difference (reduction or increase) is found to be proven according to the alternative hypothesis.

All secondary outcomes are purely exploratory, where effects are looked at and no Null Hypothesis is tested. This study is designed to get an idea of the effect size, since an estimation of the effect size is needed in order to calculate the sample size of a subsequent confirmatory study.

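### Section 5.1 says the LDQ result will verify efficacy, but a single-arm test against zero change can show only that symptoms changed, as section 6.1 itself says

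*Protocol*

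**What the plan says.** The protocol describes the purpose of the primary result in two ways.

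**As evidence of efficacy.** Section 5.1: "the LDQ variable will be the main result to verify whether the test medication in this trial is efficacious". The synopsis rationale for the number of participants opens its 60% criterion with "To demonstrate convincing evidence of clinical efficacy", and the synopsis labels the trial confirmatory, phase IV.

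**As a description of change.** Section 4.2 sets out to document perceived changes in symptoms between visits 1 and 3. The limitations in 6.1 say "This study design does not allow evaluating the efficacy of Amara medication" and that the results are to inform a later randomised study. Section 11.1 says "an estimation of the effect size is needed in order to calculate the sample size of a subsequent confirmatory study", which places confirmation in another trial.

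On the design, the synopsis records "No control group", and randomisation and blinding are not applicable (6.2.1, 6.2.2). The sentence in 5.1 directly after the efficacy clause begins "In this open-label study in which placebo and treatment effects are summed". The null hypothesis in 11.1 is "There will be no difference in the primary outcome (LDQ score) between baseline and after four weeks of Amara treatment", tested at two-tailed p ≤ 0.05 (11.4). On significance, 11.1 calls the difference proven.

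The 6.1 limitations expect a large placebo effect and say that the power calculation takes it into account.

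**The concern.** The primary endpoint is a self-reported, open-label, before-after change. It contains drug effect, placebo response and natural course together, and nothing in the design separates them. Regression to the mean also enters, because 5.1 measures from visit 1, where an LDQ cut-off selects patients (7.2). A sum cannot verify one of its parts, so 5.1 claims something the design cannot deliver.

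The interpretation of the primary result is at stake. The section that defines the primary outcome and the section that lists the limitations give opposite instructions. An author who reports a significant change as verified efficacy could cite 5.1; one who declines to do so could cite 6.1. The protocol should settle this before results are interpreted.

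**Working it through.** **1. The plan's own figure, and whether it contains a placebo term.** Section 11.2 gives 58 patients from d = 0.4, power 0.9 (printed as beta) and alpha < 0.05; 11.4 makes the test two-tailed. For a paired comparison:

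n = ((z for alpha + z for power) / d)²

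- Two-sided 0.05: ((1.960 + 1.282) / 0.4)² = 65.7, so 66 patients, or 68 with the t distribution.
- Two-sided 0.01 (the alpha in 3.8 and the synopsis): ((2.576 + 1.282) / 0.4)² = 93, or 97 with t.
- One-sided 0.05: 53.5, so 54, or 55 with t. Dividing 55 by the Wilcoxon efficiency 0.955 gives 57.6, so 58. This was the only paired variant tried that reached 58, and it conflicts with the two-tailed analysis.

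The mismatch and the two alphas are separate matters. What counts here is that every variant uses only d, alpha and power, with d the total change from zero. Nothing is subtracted for placebo.

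**2. What the test requires.** With n = 60 the critical t on 59 degrees of freedom is 2.001, so an observed standardised change of 2.001 / √60 = 0.258 is already significant. Powering for 0.4 does not make 0.4 a condition for significance.

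**3. Significance with no drug effect.** Let d be the mean non-specific change in SD units of the paired difference (assumed values). The noncentrality is d√60, and power is taken from the noncentral t, two-sided 0.05.

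| Assumed non-specific d | d√60 | P(significant) |
|---|---|---|
| 0 | 0 | 0.05 |
| 0.2 | 1.55 | 0.33 |
| 0.3 | 2.32 | 0.63 |
| 0.4 | 3.10 | 0.86 |
| 0.5 | 3.87 | 0.97 |

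**4. How far the protocol fixes d.** It does not. Its only figure is a placebo effect in up to 40% of patients (11.2), a proportion that becomes a d only with an assumed size of response. If 40% of patients improve by 0.5, 1.0 or 1.5 SD and the rest do not change, simulation gives P(significant) of about 0.32, 0.78 or 0.96.

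**5. The 60% benchmark.** Read as at least 0.6 × 60 = 36 improved patients, it would be met with exact binomial probability of about 0.001 at a true placebo response of 40%, and about 0.08 at 50%. It is therefore far stricter than the t-test. But 11.1 tests zero mean change and 11.4 sets only the p-value threshold; the benchmark appears in neither.

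**The case against.** The protocol is candid elsewhere. Its title, section 4.2 and the opening of 5.1 speak of perceived change. Section 6.1 warns of a large placebo effect and rules out an efficacy evaluation. The efficacy clause in 5.1 follows a paragraph on validation of the scale, so it partly justifies the choice of instrument. The only efficacy criterion with a number is the 60% response rate in the synopsis, which a 40% placebo response would rarely meet.

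Most of this stands, and it limits the point. A reader might infer that p ≤ 0.05 counts as a declaration that Amara works, and that the probabilities above are rates of false efficacy claims. The documents do not support that: 11.1 says only that the difference, in either direction, is proven. The table gives chances of a significant change under assumed values.

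A reader might also conclude that the whole trial should be relabelled exploratory. That does not follow either, because 11.1 calls only the secondary outcomes purely exploratory and keeps a formal primary hypothesis.

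These points do not rescue the efficacy clause itself. The disclosure in 6.1 contradicts 5.1 without overriding it. The safeguard claimed in 6.1 is absent from the calculation in 11.2. The benchmark has no place in the decision rule and, even if met, would be compared with a cited placebo rate, not a concurrent control.

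**Conclusion.** The contradiction is real and stands in current text: 5.1 and the synopsis claim for the primary result what 6.1 says the design cannot give, and the confirmatory label conflicts with 11.1. The primary test can establish a change in perceived symptoms, not its cause. The statement that placebo is covered by the power calculation is not borne out by 11.2.

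The size can only be illustrated. With no drug effect, significance has probability of about 0.63 to 0.97 for an assumed non-specific change of 0.3 to 0.5 SD, and 0.05 if there is no such change. This rests on 60 analysed patients, the paired t-test and the assumed d.

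This is a fault of wording and interpretation that should be fixed. The endpoint, sample size and test are not faulted by this point.

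**What to change.** - **5.1:** replace the efficacy clause with *to estimate and test the change in perceived symptom burden over 4 weeks of Amara*, in line with 4.2.
- **Synopsis, rationale for number of participants:** replace the reference to clinical efficacy with convincing change in perceived burden, as 3.8 and 11.2 already have it. Keep the 60% benchmark as a descriptive comparison with the cited placebo response, and say that it is not proof of efficacy.
- **6.1, limitations:** remove the statement that the power calculation accounts for the placebo effect.
- **Synopsis, clinical phase:** reconcile the confirmatory label with 11.1.
- **11.1:** add that a significant change does not show efficacy of Amara, and that the estimate with its 95% confidence interval informs the later randomised trial.

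The primary hypothesis and its two-tailed 0.05 test stay unchanged. The cost is a wording amendment in a few places, with no effect on data, procedures or patients. The downside is a weaker headline claim.

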5.2 Secondary Outcomes

Secondary objectives / outcome measures

- Assess perceived effect of Amara on other gastrointestinal symptoms using validated, patient related outcome measurements (reflux disease questionnaire, IBS Symptom Severity Score)
- Assess effect of Amara on (i) visceral sensitivity and (ii) gastric emptying (¹³C-breath test) in
 patients with functional dyspepsia with validated 400ml Liquid Nottingham Test Meal. Details
 of the acquisition and analysis of these physiological measurements are in the appendix
 (SOP). (iii) gastric electrical activity before, during and after the test meal as assessed by the
 Gastric Alimetry System (concurrent measurements of heart rate will also be acquired)

• Overall satisfaction with Amara treatment will be assessed by a 100mm visual analogue scale and whether ongoing prescription is wanted (yes/no).

5.3 Other Outcomes of Interest

The validity of the Lüscher Colour Test (LCT) in the assessment of patients with functional dyspepsia will also be assessed. This will include face validity (debriefing session), construct validity (comparison with validated questionnaires assessing psychological patient related outcome measures), reproducibility (test re-test validity before and after run-in period), and internal consistency. Sensitivity of LCT to any change in dyspeptic symptoms, psychological or physiological state that occurs during the treatment study will also be documented.

5.4 Safety Outcomes

All perceived events and side effects will be entered by the participant when filling in the questionnaire. In addition, they will report any SAE to the study team by use of the mobile application or telephone (even after study end/discontinuation until the adverse effect subsides).

Previous placebo-controlled trials that studied the effects of another aromatic bitter preparation in patients with dyspepsia reported side effects similar to placebo.(11) Additionally, safety monitoring has identified very few ADRs in the last 15 years (see section 3.4). Participants can indicate possible side effects in the questionnaire booklet. Furthermore, participants are instructed to report the start and duration, the severity (minor, moderate, severe) of the side effect and what have been done about it.

6. STUDY DESIGN

6.1 General study design and justification of design

The present IIT (Investigator-Initiated Trial) study is a prospective, open, monocentric, single arm, intervention study (phase IV) of the category A, as defined in the Ordinance on Clinical Trials in Human Research (ClinO) of 20 September 2013 (D. S. Bundesrat, "Verordnung über klinische Versuche in der Humanforschung," vol. 2013, no. September, pp. 3407–3454, 2013), on the basis of the Human Research Act (HRA) of 30 September 2011 (Die Bundesversammlung der Schweizerischen Eidgenossenschaft, "Bundesgesetz über die Forschung am Menschen (Humanforschungsgesetz, HFG)," vol. 1313, no. September, pp. 1–26, 2011).

A past survey showed that among Anthroposophical physicians the most frequent diagnosis group where Amara preparations are prescribed are gastrointestinal disorders such as dyspepsia and irritable bowel syndrome (Eva-Med Network 2009, data on file); however, prospective clinical studies have not been performed. In the present study we therefore want to investigate the effectiveness of Amara drops in patients with functional dyspepsia diagnosed according to Rome IV criteria.(1)

Study participants will be recruited among the patients referred to the Department of Integrative Gastroenterology at the Clinic Arlesheim. Recruitment period will last 18 months. This duration is very cautiously estimated with basis on expected at least two referrals for assessment of dyspeptic symptoms per week. Best clinical care will be provided regardless of whether the patient is eligible and / or consents to participate in the study.

At the initial screening assessment at Clinic Arlesheim, patients will be informed about the study by one of the research team. If the participants fulfil the inclusion criteria and consent to participate, then the team member will administer the questionnaires and help the participant download the mobile application to monitor symptoms onto their smart phone (paper version available). Participants who signed the informed consent form will fill in a questionnaire with questions about dyspeptic (LDQ) and other gastrointestinal symptoms (RDQ, IBS-SSS), anxiety and depression (HADS), somatization (PHQ15), the Internal Coherence Scale (ICS) and the Lüscher Colour Test (LCT).

An appointment will be made 2-4-weeks later for the second study visit at which time the ¹³C gastric emptying study will be performed again. The run-in period is 2-4-weeks. This reduces the influence of spontaneous "regression to the mean" (i.e., false positive results).(15)

Gastric motor and sensory function will be assessed by ingestion of the 400ml, 300kcal Nottingham Test Meal (NTM) labelled with ¹³C acetate. This provides both an assessment of patient symptoms / visceral sensitivity to gastric filling with the 400ml liquid nutrient meal and also an assessment of gastric emptying. The 400ml NTM can be ingested by >95% of patients with functional dyspepsia.(19,

24) The ¹³C isotope is not radioactive, it takes 2-hours to complete and this technique is very appropriate for repeated assessment of gastric emptying.(16) In a subset of 20 consecutive patients, gastric electrical activity will be measured before, during and after ingestion of the Nottingham Test Meal using the non-invasive Gastric Alimetry System (high-resolution gastric mapping / electro-gastrography). Concurrent heart rate monitoring will provide an assessment of cardiovagal tone / autonomic nervous function.

The treatment period with Amara drops is four weeks per patient; participants will be instructed to take 10-20 drops of the herbal medicine Amara three times a day before meals over 28 days. This treatment period is in accordance with previous studies for aromatic bitter substances and represents the minimum recommendation for study duration in functional gastrointestinal disorders.(15) During the treatment period patients will record their symptoms using a mobile application (reminder will be sent at 21:00 every day). In addition, patients can note side effects that they perceive to be caused by Amara. If participants do not regularly provide this information, then a team member will call to ask if they have any problems.

At the end of the treatment period the participant will return to Clinic Arlesheim for repeat assessment. The LDQ and other patient related outcomes will be assessed again and ¹³C gastric emptying study will be repeated on treatment.

At the end of the study, all participants will return the supply of Amara. The study team will assess compliance by counting the empty bottles and weighing partly used bottles. Patients will be asked whether they wish to continue the medication (yes / no). If the response is positive, then ongoing treatment will be recommended. Amara is classified by Swissmedic as dispensing category D available following discussion with specialist without prescription ("Abgabekategorie D: «Abgabe nach Fachgespräch»).

Overall, approximately 30 minutes will be needed to complete the questionnaires on each occasion. The total time required per patient during the study is a maximum of 8 hours (reading documents, filling in questionnaires, gastric emptying study (twice)).

During the period the participants are enrolled in this study no additional outpatient examinations are planned. If, while someone is participating in the study, acute symptom occur and the need arises for early outpatient assessment or inpatient admission to the clinic, the study would be terminated for this subject as of this date.

Limitations:

- The study will provide a prospective assessment of perceived treatment effectiveness; however, a large non-specific (placebo) effect is likely to be present as in any open-label, single-arm study in patients with functional gastrointestinal disease. This limitation is factored into the power calculation which requires at least a moderate treatment effect for Amara to be considered effective. Note that the secondary analysis that will identify baseline factors (e.g., age, sex, symptom severity, gastric emptying rate) that associate with treatment effect will be relatively less sensitive to this confounding factor.
- In addition to subjective patient related outcome measures, repeat ¹³C breath testing with the Nottingham Test Meal on and off treatment will provide physiological assessment of effects of Amara on gastric motor and sensory function. Continuous assessment of patient sensations during Drink tests (i.e., gastric filling) may be less impacted by patient recall than questionnaires. ¹³C breath testing provides an indirect assessment gastric emptying based on the excretion of ¹³CO₂ in the expired air. Although well validated against scintigraphy, it remains uncertain to what extent these results can be affected by individual patient factors other than gastric emptying (e.g. metabolism). Note that this limitation will not affect the results of this study because we will compare gastric emptying in patients on and off Amara treatment (i.e., patients act as their own control).
- Amara drops will be distributed for self-administration at home, thus, we rely on participants to report their intake accurately. Compliance will be checked as described above.
- The four-week duration of drug intake is relatively brief and may underestimate the treatment effect.
- This study may suffer from the limitation that participants will take other over the counter medications or engage in other treatments at home.
- This study design does not allow evaluating the efficacy of Amara medication. However, the aim of this prospective study is to acquire results on overall effectiveness that will inform the design of a randomized controlled study with this aim.

